Sanofi Pasteur's CoV2 preS dTM-AS03 vaccine is being developed in the setting of a pandemic for the active immunization and prevention of SARS-CoV-2 infection and COVID-19 disease. The initial intended use of the vaccine is for adults, 18 years of age and older. Studies including pediatric populations will be completed later since this population is at lower risk to develop severe complications. A study to evaluate safety and immunogenicity in pregnant females will also be completed later once results of nonclinical development and reproductive toxicity are available and initial results demonstrating safety and a positive benefit-risk in humans are available.

The candidate antigen is a stabilized prefusion trimer of the SARS-CoV-2 S protein. The coronavirus S protein is the major viral envelope glycoprotein and mediates attachment and entry into host cells. The S protein precursor is cleaved to form non-covalently associated subunits, S1 and S2 (19). The S protein appears on the surface of the virus as a mushroom-like structure, containing a cap of three S1 subunits and a stem of three S2 subunits. The S1 subunit contains the receptor binding domain (RBD), which attaches to the host cellular receptor. In the case of SARS-CoV-2, the receptor is Angiotensin Converting Enzyme-Related Peptidase 2 (ACE2), a membrane-bound carboxypeptidase localized to vascular endothelial as well as epithelial surfaces (20). The RBD is a major antigenic target for immune responses. The S2 domain contains the fusion peptide and transmembrane regions. Upon binding to the cellular receptor, S1 is cleaved from the virus and the S2 subunit undergoes a conformational change to mediate viral membrane fusion with the host cell membrane.

Prior research with Middle East Respiratory Syndrome (MERS)-CoV identified that the introduction of double proline substitutions (2P) at the beginning of the central helix of the S2 subunit could stabilize the structure and prevent conformational changes in the S trimer (21). When used to immunize mice, the MERS-CoV 2P construct was associated with improved breadth and potency of neutralizing responses compared to monomeric MERS-CoV S1 or wild-type S. This strategy was identified as being of general relevance to betacoronaviruses, which include HCoV-OC43, MERS-CoV, and SARS-CoV-1, and by extrapolation to SARS-CoV-2 (10). The prefusion stabilized SARS-CoV-2 S construct to be evaluated in the current study is based on this research.

The S1 subunit and RBD of the prefusion SARS-CoV-2 S antigen used in this vaccine is similar in sequence to the S antigens encoded by the mRNA vaccine constructs that have been shown to induce neutralizing antibody responses and confer robust efficacy against COVID-19 (7) (8), suggesting that other vaccines capable of inducing similar levels of neutralizing antibodies may also provide protection.

The antigen will be manufactured using the same technology as is used to manufacture a recombinant quadrivalent influenza vaccine (rQIV), licensed in the US and EU and commercialized as Flublok® and Supemtek®, respectively for the prevention of influenza in adults 18 years of age and older (22). In this manufacturing platform, the gene of interest is cloned into a baculovirus transfer vector, which is used to form recombinant baculoviruses. The viral stock is used to infect an insect cell line (expresSF+). The recombinant protein is expressed in the infected insect cells. After incubation, the recombinant protein is purified by a series of filtration and chromatography steps. This process is adaptable to manufacture a variety of antigens. Millions of doses of recombinant influenza vaccine (trivalent and quadrivalent formulations) have been administered since its approval in the US for human use corresponding to hemagglutinins (HAs) of different influenza strains (H1, H3, and B) covering multiple influenza seasons. Additionally, the process has previously been applied to the development of candidate SARS-CoV-1 vaccines. Following the SARS outbreak, candidate S protein vaccines were developed, including a full-length S protein and a transmembrane-deleted ectodomain antigen. These were tested in a variety of preclinical models and found to induce neutralizing antibody responses in mice and ferrets and to be partially protective in a ferret challenge model.

The magnitude and quality of the immune response to the candidate antigen will be enhanced through delivery with an adjuvant. In addition, the adjuvant may influence the quality of the

immune response. Previous clinical studies with rH5 HA and rH7 HA pandemic antigens in naïve individuals show that a 2-dose immunization regimen of antigen was poorly immunogenic in comparison to antigen delivered with an adjuvant (23). This may allow for titration of the amount of antigen used and, thus, be antigen-sparing and potentially increase the available supply of antigen doses.

AS03 is an oil-in-water emulsion containing α -tocopherol and squalene. Safety of AS03-adjuvanted products has been extensively evaluated and found to be generally well tolerated with an acceptable safety profile (24). AS03 has been approved as a component of Pandemrix and Arepanrix, two H1N1 pandemic influenza vaccines. AS03 was also evaluated with pandemic H7 rHA in humans, demonstrating robust neutralizing antibody responses and hemagglutination inhibition, together with an acceptable safety profile. As has been the case for several pandemic agents, unadjuvanted H7 HA-containing influenza vaccines were poorly immunogenic (25) (26). In addition to a Phase I/II study using the Sanofi Pasteur CoV2 preS dTM antigen with AS03-adjuvanted system (NCT04537208), AS03 has also been used in combination with other AS03-adjuvanted recombinant S proteins (Medicago [NCT04450004] (27) and Clover Biopharmaceuticals [NCT04405908]).

A potential (yet theoretical) safety concern with coronavirus vaccines is the ability to potentiate immunopathology in vaccinees upon exposure to wild-type virus (28), called vaccine associated enhanced disease (VAED). The theoretical molecular mechanism for this phenomenon, is also not fully understood. In the context of coronavirus infections, various factors have been suggested as potentially contributing to the phenomenon. These include the epitope targeted, the method of delivery of the antigen, the magnitude of the immune responses, the balance between binding and functional antibodies, the elicitation of antibodies with functional characteristics such as binding to particular Fc receptors, and the nature of the Th cell response (29) (30) (31). It is anticipated that the design of the candidate CoV2 preS dTM antigen selected for this study will promote generation of robust neutralizing antibodies over binding but non-neutralizing antibodies, based on data generated with other coronavirus vaccine antigens (10) (21). The inclusion of adjuvanted formulation is anticipated to further enhance the magnitude of neutralizing antibody responses and induce balanced Th1/Th2 cell responses (32) (23). Taken together, these strategies mitigate by design the theoretical risks of immune enhancement of viral infection.

The clinical development plan gives priority to generating data in adults given the higher medical and public health need in this population compared to the pediatric population; pediatric studies are proposed to be de-linked from the critical path to first authorization/approval. Importantly, the Phase II study is designed to be pragmatic to maximize representation of a broader population by minimizing exclusionary eligibility criteria and allowing the participation of individuals with a range of medical conditions including controlled HIV infection, Hepatitis B, Hepatitis C, and conditions associated with an increased risk of severe COVID-19. It is also designed to be inclusive of other subpopulations affected by COVID-19, including older adults as well as ethnic and racial minorities.

The clinical development plan for CoV2 preS dTM-AS03 vaccine began with a Phase I/II study (VAT00001) in adults with the goal of identifying a formulation, antigen dose, and a dosing schedule for further development. In the VAT00001 study, the safety and immunogenicity of a low-dose and high-dose antigen formulation corresponding to effective doses of 1.3 μ g and 2.6 μ g, respectively, of purified recombinant SARS-CoV-2 S-protein with AF03 and AS03

adjuvant administered either as a single injection or 2 injections 21 days apart are being evaluated. Interim results of the VAT00001 study support the selection of the AS03 adjuvant system and a 2-injection schedule but also indicate that further optimization of the antigen formulation and dosage is needed. Data from the VAT00001 study have informed the design of this Phase II study (VAT00002) aiming at selecting a suitable antigen dose adjuvanted with AS03 in a 2-injection schedule for further progression to a Phase III study.

A Phase II/III study in the pediatric population is planned to be initiated following generation of evidence in adults of a favorable benefit-risk of the vaccine. A Phase III study to assess the safety and immunogenicity of the vaccine in pregnant women is also planned after availability of a nonclinical DART (Developmental and reproductive toxicity) study and interim safety and immunogenicity data from the Phase II study in adults.

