§ These samples will be collected only from a subset of participants in Cohort 2 who received the Pfizer/BioNTech vaccine priming series only.

§§ Participants will use this DC1 to record information about solicited reactions, unsolicited AEs, SAEs, MAAEs, and AESIs from D01 to D15 after vaccination and will continue to record information about unsolicited AEs, SAEs, MAAEs, and AESIs from D16 to V03. In addition, the participant will use the DC to report the information related to COVID-19-like illness.

*** The Investigator or an authorized designee will remind the participants to bring back the DC at the next visit and will answer any questions.

††† The Investigator or an authorized designee will interview the participants to collect the information recorded in the DC and will attempt to clarify anything that is incomplete or unclear.

†††† Participants will use this DC2 to record SAEs, MAAEs, and AESIs. In addition, the participant will use the DC to report the information related to COVID-19-like illness.

§§§ Participants will use this DC3 to record SAEs, MAAEs, AESIs, and information related to COVID-19-like-illness from V04 to V06.

**** AESIs (serious and non-serious) will be collected throughout the study and will be communicated to the Sponsor in an expedited manner similar to the reporting of SAEs and followed-up until the end of the follow-up period or resolution, as per the assigned causality. These include: Anaphylactic reactions, Generalized convulsion, Thrombocytopenia, Thrombosis with thrombocytopenia syndrome, Myocarditis, Pericarditis, and potential immune-mediated diseases (pIMDs).

†††† In case of participant discontinuation at a visit, the entire visit will be completed.

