Supplemental Cohorts Subsets and Assessment of Immunogenicity to Emerging Variants of Concern: A randomized subset of 70 participants in Cohort 1 will be tested for additional SARS-CoV-2 variants of concern including Delta. No additional sample collection, procedures, or visits are required for this subset. A randomized subset of 82 participants in Cohort 2 comprised of younger adults (18 to 55 years of age) will provide samples for cellular immune response and mucosal antibody assessments and will also be tested for additional variants of concern including Delta.

For all cohorts: blood samples collected from all participants will be used for serological assessments in the study. Whole blood, PBMCs, and saliva samples will be collected from a subset of participants in each cohort to assess cellular immune responses and mucosal antibody responses.

Reactogenicity will be assessed by collecting solicited AEs for 7 days after each vaccination, unsolicited AEs for 21 days after the last vaccination, and SAEs, MAAEs, and AESIs for the duration of the study.

All Supplemental Cohort participants will be followed for the duration of the study to capture occurrences of COVID-19 through passive surveillance wherein participants will be instructed to contact the site if they experience symptoms/conditions of a COVID-19-like illness at any time during the study. In addition, active surveillance will be undertaken in all participants wherein all participants will be contacted once every 2 weeks starting after the last injection to enquire about development of COVID-19-like illness.

The duration of participation in the study for each participant will be:

- Supplemental Cohorts 1 and 2: approximately 365 days post-booster injection (ie, approximately 366 days total)
- Supplemental Cohorts Comparator Group: approximately 365 days post-injection 2 (ie, approximately 386 days total)

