Eligible participants who have received the Pfizer/BioNTech vaccine will be first assigned to the non-exploratory groups (ie, main arms, N = 1130), and will be randomized in a 1:1 ratio to receive a single injection of either the CoV2 preS dTM-AS03 (B.1.351) booster vaccine or the CoV2 preS dTM-AS03 (D614 + B.1.351) booster vaccine. Randomization will occur by age strata (1030 [515 per group] belonging to the 18-55 years of age group, and 100 [50 per group] belonging to the 56 years of age and older group). A subset of 5% of participants aged 18-55 years old (~26 participants in each of these 2 Booster Groups) will be randomly assigned to collect CMI

and mucosal samples plus variant testing. Once enrollment for the main arms has been completed for the Pfizer/BioNTech-primed individuals, eligible individuals who have received this vaccine will be randomized in a 1:1:1:1 ratio into one of the four Monovalent B.1.351 exploratory groups (total N = 400) as described in [Section 4.1](#) No CMI and mucosal samples will be collected in these exploratory groups.

Eligible participants who have received the Moderna (N = 200), Oxford University/Astra Zeneca (N = 200), or J&J/Janssen (N = 200) vaccines will be randomized in a 1:1 ratio to receive a single injection of either the CoV2 preS dTM-AS03 (B.1.351) booster vaccine or the CoV2 preS dTM-AS03 (D614 + B.1.351) booster vaccine. Randomization will occur by age strata (with ¾ of participants belonging to the 18-55 years of age group). No CMI and mucosal samples will be collected in these groups.

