Eligible participants transitioning from the VAT00002 Original Phase II Cohort who have received the CoV2 preS dTM-AS03 (D614) candidate vaccine (targeted N = 450; actual number to be determined by number of VAT00002 participants meeting eligibility criteria for transition) will be randomized to receive a single injection of either the CoV2 preS dTM-AS03 (D614) or the CoV2 preS dTM-AS03 (B.1.351) booster vaccine. Randomization will occur by age strata (assumption that about 2/3 of participants will be 18-55 years of age (ie, 300 adults 18-55 years old, allocation ratio of 9:1 between CoV2 preS dTM-AS03 [D614] group and the CoV2 preS dTM-AS03 [B.1.351] group); the actual number and age distribution will be determined by characteristics of those who meet eligibility criteria for transition). A subset of 10% of participants aged 18-55 (~30 participants in the 2 Booster Groups combined) will be randomly assigned to collect CMI and mucosal samples plus variant testing.

Site staff will connect to the IRT system, enter the identification and security information, and confirm a minimal amount of data in response to IRT prompts. The IRT will collect information on age-group, priming vaccine, high-risk medical conditions, and ethnicity/race (the last 2 for monitoring purposes and high-risk medical conditions for potential capping). The IRT will then provide the group assignment (intervention arm and CMI/mucosal subset [if applicable]). The full detailed procedures for group allocation are described in the Operating Guidelines.

Supplemental Cohorts Comparator Group:

This Group will be open-label and not randomly assigned as all eligible participants will have common baseline characteristics (previously unvaccinated) and all will receive two injections of the CoV2 preS dTM-AS03 (D614) candidate vaccine 21 days apart. Eligible participants must be 18-55 years of age and have a negative baseline SARS-CoV-2 rapid serodiagnostic test to be enrolled into this group. A subset of 5% of participants aged 18-55 (~26 participants) will be randomly assigned to variant testing subsets.

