In addition, for the primary series, if a participant seeks an authorized/approved vaccine, they will be invited to a visit prior to receiving the vaccine and invited to provide a blood sample for immunological assessment. If the visit occurs more than 1 month after the D134 visit, a PBMC sample will also be collected if the participant is in the cellular immunity and mucosal subset instead of the D387 sample (D366 for groups receiving booster vaccine).

Guidance and information for the sample collection, preparation, storage, and shipment are provided in the Operating Guidelines.

Table 8.1: Original Phase II Cohort: samples collected per visit

	D01	D22	D36	D78	D134	D202	D292	D387
Vaccination	X	X						
	BL0001	BL0002	BL0003	BL0004	BL0005	BL0006	BL0007	BL0008
SARS CoV2 Microneutralization assay (SP)	X	X	X	X	X	X	X	X
Anti-S IgG ELISA	X	X	X	X	X	X	X	X
SARS-CoV-2 Pseudovirus Neutralization Assays	X	X	X	X	X	X	X	X
ECLIA Multiplex Assay			X					
Anti-N Immunoassay	X	X	X	X	X	X	X	X
Anti-S Immunoassay	X							
SARS-CoV-2 NAAT on nasopharyngeal sample	X	X						
SARS-CoV-2 NAAT on respiratory sample during a COVID-19-like illness								
Rapid SARS-CoV-2 serodiagnostic Test	X							
Whole Blood TruCulture assay	X	X	X					
Flow Cytometry and Intracellular Cytokine Staining	X	X	X		X			X*
B-cell memory Fluorospot	X				X			X*
Saliva samples	X	X	X		X			

SP, Sanofi Pasteur

*If a participant seeks an authorized/approved vaccine, they will be invited to a visit prior to receiving the vaccine. If the visit occurs more than 1 month after the D134 visit, a PBMC sample will also be collected if the participant is in the cellular immunity and mucosal subset instead of the D387 sample.

Table 8.2: Participants in Supplemental Groups receiving a single booster dose: Cohort 1, Cohort 2 Main Arm, Cohort 2 Exploratory B.1.351 Arm: samples collected per visit

	D01	D15	D29	D91	D181	D366
Vaccination	X					
	BL0001	BL0002	BL0003	BL0004	BL0005	BL0006
Anti-S IgG ELISA	X	X	X	X	X	X
SARS-CoV-2 Pseudovirus Neutralization Assays	X	X	X	X	X	X
SARS-CoV-2 Pseudovirus Neutralization Assays Variants of Concern	X	X	X		X	X
ECLIA Multiplex Assay	X		X			
Anti-S Immunoassay	X					
SARS-CoV-2 NAAT on nasopharyngeal sample	X					
SARS-CoV-2 NAAT on respiratory sample during a COVID-19-like illness	Illness visit (see Section 8.3.3)					
Flow Cytometry and Intracellular Cytokine Staining	X		X	X		X
B-cell memory Fluorospot	X			X		X
Saliva samples	X	X		X		

SP, Sanofi Pasteur

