**PBMC collected only in Cohort 2

Table 8.3: Participants in Supplemental Cohorts Comparator Group receiving 2-dose schedule: samples collected per visit

	D01	D22	D36	D134	D202	D292	D387
Vaccination	X	X					
	BL0001	BL0002	BL0003	BL0004	BL0005	BL0006	BL0007
Anti-S IgG ELISA	X	X	X	X	X	X	X
SARS-CoV-2 Pseudovirus Neutralization Assays	X	X	X	X	X	X	X
SARS-CoV-2 Pseudovirus Neutralization Assays Variants of Concern	X		X		X		X
Anti-S Immunoassay	X						
SARS-CoV-2 NAAT on nasopharyngeal sample	X	X					
SARS-CoV-2 NAAT on respiratory sample during a COVID-19-like illness	Illness visit (see Section 8.3.3)						
Rapid SARS-CoV-2 serodiagnostic Test	X						
B-cell memory Fluorospot**	X			X			X*
Saliva samples	X	X	X	X			

SP, Sanofi Pasteur

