8.2.3.2 Cellular Immune Assays

These assays will be done in the subset of participants belonging to the cellular immunity and mucosal subset in whom PBMCs will be collected. These subsets will be selected for the Original Phase II Cohort and for Supplemental Cohort 2 as described in [Table 8.2](#) and [Table 8.3](#). B cell memory responses using a multiplexed B cell FluroSpot assay evaluating IgG and IgA specific B cells to S protein will be measured at D01, D134, and D387 in the Original Phase II Cohort and D01, D91, and D366 in the Booster Cohort in vaccinees and D01, D134 and D387 in the Booster Cohort in naïves.

Multiparametric flow cytometry will be used to identify antigen-specific CD4+ and CD8+ T-cells following stimulation with S protein or S-antigen peptide pools is planned in the subset of participants belonging to the cellular immunity and mucosal subset at D01, D22, D36, D134, and D387 in the Primary series, D01, D15, D29, D91 and D366 in the Booster Cohort in vaccinees and D01, D22, D363, D134 and D387 in the Booster Cohort in naïves. Preparation of blood samples and shipping instructions for cellular immunology assays are outlined in the Operating Manual.

Timepoints for these assessments are specified in [Table 8.1](#), [Table 8.2](#), and [Table 8.3](#).

Preparation of blood samples and shipping instructions for cellular immunology assays are outlined in the Operating Manual.

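### The Table 1.2 footnote limits PBMC and saliva sampling to Pfizer/BioNTech-primed participants, although about 30 of the 82 in the Cohort 2 cellular/mucosal subset are protein-primed; Table 8.2 also omits the D15 flow cytometry assay

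*Protocol*

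**What the plan says.** **Who is sampled.** Section 4.1.2 sets the size of the subset: "A randomized subset of 82 participants in Cohort 2 comprised of younger adults (18 to 55 years of age) will provide samples". Section 6.3.1 builds it from two sources. The first is the two Pfizer/BioNTech-primed main arms: "A subset of 5% of participants aged 18-55 years old (~26 participants in each of these 2 Booster Groups"). The second is participants who move over from the Original Phase II Cohort after the protein vaccine; 10% of those aged 18-55 "will be randomly assigned to collect CMI and mucosal samples plus variant testing". Table 4.5 shows the same split: 52 Pfizer/BioNTech-primed and 30 protein-primed, the latter being 27 with the D614 booster and 3 with the B.1.351 booster. The definition of the CMIAS in Section 9.3 names both groups.

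The Schedule of Activities for the booster arms (Table 1.2) carries a footnote on the PBMC and saliva rows: "These samples will be collected only from a subset of participants in Cohort 2 who received the Pfizer/BioNTech vaccine priming series only". Section 8 states that adherence to the schedules is required and that waivers are not allowed.

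**When cellular assays are run.** For boosted participants, Section 8.2.3.2 gives the flow cytometry days as "D01, D15, D29, D91 and D366 in the Booster Cohort in vaccinees". Exploratory objective 3 for Cohort 2 lists the same five days, and Table 1.2 schedules a PBMC draw on each of them. In Table 8.2, the row "Flow Cytometry and Intracellular Cytokine Staining" is marked at D01, D29, D91 and D366 only.

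**The concern.** The footnote and the allocation text cannot both be followed. The word 'only' stands twice in the footnote, so it cannot be read as allowing protein-primed participants. A site that enrols such a participant into the subset holds an assignment to give PBMC and saliva, and a mandatory schedule that tells it not to take them.

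At stake are the cellular and mucosal data on the boost after protein priming, that is, after the sponsor's own vaccine. The neutralizing response to the D614 booster in that group is a conditional secondary hypothesis, so these data would help to interpret a result that the plan tests formally. A pre-boost sample that is not taken at D01 cannot be taken later. The cellular data from the Original Phase II Cohort concern the primary series and do not replace it.

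The D15 discrepancy is smaller. Section 8.2.3.2 refers the reader to Table 8.2 for timepoints, and that table assigns no PBMC assay at D15: the flow cytometry row is blank there, and so is the row "B-cell memory Fluorospot" (which agrees with the B-cell days in Section 8.2.3.2). A 40 mL PBMC draw is thus scheduled on a day for which the sample table lists no use.

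**Working it through.** **Step 1. Reproduce the size of the subset** (inputs from Section 6.3.1, ages 18-55).
- Pfizer/BioNTech-primed: 5% × 515 = 25.75 per arm, about 26; two arms give 2 × 26 = 52.
- Protein-primed: 10% × 300 = 30. By booster: 10% × 270 = 27 (D614) and 10% × 30 = 3 (B.1.351).
- Total: 52 + 30 = 82. Unrounded: 25.75 + 25.75 + 30 = 81.5, which rounds to 82.

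This matches Table 4.5 and the stated 82. The figure of 82 is reached only if the protein-primed participants are counted.

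**Step 2. Apply the Table 1.2 footnote as written.**
- Sampled: 52 of 82 = 63.4%.
- Not sampled: 30 of 82 = 36.6%, that is, all 27 + 3 protein-primed participants.

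**Step 3. Compare the cellular assay days for boosted participants.**

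| Source | D01 | D15 | D29 | D91 | D366 |
|---|---|---|---|---|---|
| Exploratory objective 3, Cohort 2 | yes | yes | yes | yes | yes |
| Section 8.2.3.2, flow cytometry | yes | yes | yes | yes | yes |
| Table 1.2, PBMC draw | yes | yes | yes | yes | yes |
| Table 8.2, flow cytometry/ICS row | yes | blank | yes | yes | yes |

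D15 is the only difference, and only Table 8.2 departs from the rest. The blank is read from an extracted table, but the row has all six of its day columns and looks intact.

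**Step 4. Check whether the Comparator Group is meant to give these samples.** Table 8.3 lists B-cell and saliva rows for it, and Sections 8.2.3.2 and 8.2.3.3 give days for naïve participants in the booster cohort. Section 4.1.2 speaks of a subset in every cohort, where the synopsis limits it to Cohort 2. Section 7.1.2 also mentions a replacement PBMC sample in a sentence that names the Comparator arm. Against this:
- cellular and mucosal objectives 3 and 4 are headed Supplemental Cohort 2;
- Table 4.5 and Section 6.3.1 give the 26 Comparator subset participants variant testing only;
- the CMIAS does not include the Comparator;
- Table 1.3 has no PBMC or saliva row;
- a footnote printed just above Table 8.3 limits PBMC to Cohort 2.

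The objectives, the subset and the analysis set thus agree that no Comparator cellular or mucosal data are planned. The entries in Table 8.3 and Section 8.2.3 are stray text.

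**The case against.** The strongest reply is that subset membership does not depend on a site reading a footnote. Under Section 6.3.1 the IRT gives the site the cellular/mucosal subset assignment along with the intervention arm, and the leading digit of the participant identifier marks the subset. Visit procedures are detailed in Operating Guidelines that are not at hand. A protein-primed subset member would therefore be flagged at enrolment. This stands in part: it lowers the chance of loss. It does not remove the conflict, because the flag and the binding schedule then give opposite instructions.

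The numbers are also planning figures. Table 4.5 is headed as approximate, and the protocol says that the protein-primed counts are estimates that may change. That stands, and the 37% should be read so. The role of these participants in variant testing is untouched, because the footnote covers PBMC and saliva only.

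Three stronger readings are tempting, and the protocol does not support them:
- A reader might infer that D15 samples will not be drawn. Table 1.2 schedules the draw, in line with objective 3 and Section 8.2.3.2; only the assay mark in Table 8.2 is missing.
- A reader might infer that a Comparator benchmark for cellular and mucosal responses is lost. None is planned (step 4 of the working), so it should not be counted as lost data.
- A reader might infer that data on the protein-primed boost will certainly be absent. The IRT assignment makes that a possible outcome of conflicting instructions and no more.

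**Conclusion.** The contradiction is real and stands in the current text. Table 1.2 excludes a group that Section 6.3.1, Table 4.5, the 82-participant statement and the CMIAS definition all include. If sites follow the schedule as written, about 30 of 82 subset participants (37%) give no PBMC or saliva, and these are all of the protein-primed ones. This rests on the planned numbers and on the footnote prevailing over the IRT assignment; the actual loss could lie anywhere from none to all 30.

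The D15 point is a separate and minor one: one of five planned flow cytometry days is missing from Table 8.2, with the assay at risk and the draw in place.

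All endpoints concerned are exploratory. No primary or conditional secondary test, alpha or power is affected. The correction is worth making because it is nearly free and missed samples cannot be recovered.

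**What to change.** 1. In Table 1.2, extend the footnote on the PBMC and saliva rows to cover both the Pfizer/BioNTech-primed main arms and the CoV2 preS dTM-AS03-primed participants assigned to the subset.
2. In Table 8.2, add D15 to the flow cytometry/ICS row.
3. As editorial clean-up, delete the B-cell and saliva rows from Table 8.3 and the days for naïve participants of the booster cohort from Sections 8.2.3.2 and 8.2.3.3. Align Section 4.1.2 with the synopsis so that both limit PBMC and saliva collection to a subset of Cohort 2, and check the Comparator reference in Section 7.1.2 at the same time.

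The cost is a change to tables and text. Items 1 and 2 restore what the allocation text and the objectives already plan, and item 3 removes entries that no objective uses. No participant, visit or sample is added to what Section 6.3.1 and Table 4.5 foresee. Since an unsampled visit cannot be repaired, sites should be told of item 1 without waiting for the next full amendment, so far as the approval rules allow.
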